10.3 Definition of Baseline

For the Safety Population baseline will be the last value prior to first administration of ARCT-021 in Study ARCT-021-02.

For the Longitudinal Safety Population baseline will be the last value prior to first administration of ARCT-021 as it occurred in either the ARCT-021-01 or ARCT-021-02 study.

For the Immunogenicity Population: baseline will be defined as follows.

- Baseline for Cohort 1a and 1b: Day 1 of ARCT-021-02 study
- Baseline for Cohort 2a, 2b, 2c, 2d: Day 1 of ARCT-021-01

10.4 Interim Analysis

Interim analyses of the data may be performed by the Sponsor or designee after all subjects have reached at least Day 29. Additional interim analyses may also be performed at other timepoints after Day 29.

10.5 Planned Methods of Analysis

10.5.1 General Approach

Statistical analyses will be primarily descriptive; no formal hypothesis testing will be conducted. Analyses will be performed using SAS® (Version 9.4 or higher).

In general, clinical data will be summarised separately by treatment group, by age group, dose level and visit (where applicable), using descriptive statistics (e.g. n, mean, standard deviation, standard error, median, minimum, maximum, first and third quartiles for continuous variables, and frequencies and percentages for categorical variables). When categorical data are presented, the percentages will be suppressed when the frequency count is zero. Non-zero percentages will be rounded to one decimal place, except 100% will be displayed without any decimal places. Statistical testing, if performed, will be prespecified in the final statistical analysis plan prior to unblinding of subject data.

10.5.2 Demographic and Baseline Characteristics

The Safety Population and Longitudinal Safety Population will be used for analyses of disposition, demographics and baseline characteristics, which will be summarised using descriptive statistics.

10.5.3 Safety Analysis

The primary objective of the study is the evaluation of the safety and tolerability of ARCT-021. The primary endpoints that align with this objective are:

- Solicited AEs for 7 days after vaccination (Cohort 1), summarized by toxicity grade
- Unsolicited AEs for 28 days after vaccination (Cohort 1), summarized by mild/moderate/severe and relationship to ARCT-021
- SAEs through Day 197 (Cohort 2; 12 months after ARCT-021 vaccination in ARCT-021-01 study), summarized by relationship to ARCT-021
- SAEs through Day 365 (Cohort 1; 12 months after ARCT-021 vaccination in ARCT-021-02 study), summarized by relationship to ARCT-021
- MAAEs through Day 197 (Cohort 2; 12 months after ARCT-021 vaccination in ARCT-021-01 study), summarized by relationship to ARCT-021
- MAAEs through Day 365 (Cohort 1; 12 months after ARCT-021 vaccination in ARCT-021-02 study), summarized by relationship to ARCT-021
- NOCDs through Day 197 (Cohort 2; 12 months after ARCT-021 vaccination in ARCT-021-01 study), summarized by relationship to ARCT-021
- NOCDs through Day 365 (Cohort 1; 12 months after ARCT-021 vaccination in ARCT-021-02 study), summarized by relationship to ARCT-021
- Safety laboratory assessments through 28 days after vaccination (Cohort 1), summarized by toxicity grade (where relevant)

- Vital signs assessments through day 365 (Cohort 1; 12 months after ARCT-021 vaccination in ARCT-021-02 study) summarized by toxicity grade

To support the continued characterization of ARCT-021 tolerability and safety when administered as a single dose, the following summaries will be provided:

- Summary of solicited (7 days after vaccination) and unsolicited AEs 28 days after vaccination)
- Summary of MAAEs, NOCDs, SAEs through 12 months after vaccination

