Any recorded temperature $\geq 38^{\circ}\text{Celsius}$ ($\geq 100.4^{\circ}\text{ Fahrenheit}$) or injection site erythema/swelling $\geq 25\text{mm}$ in size will be reported as an adverse event and graded according to Toxicity Grading Scale for Healthy Adult and Adolescent Volunteers Enrolled in Preventive Vaccine Clinical Trials, Sept 2007.

Solicited events with onset within 7 days of injection will be considered related.

Symptom diaries will be collected at the Day 8 or 15 (depending on completion status) visits for the first injection and 36 or 43 visits for the second injection and will serve as source documents.

For those subjects who received ARCT-021 in the Parent Study:

At Screening, SAEs, NOCDs, CESIs and MAAEs occurring between completion of the Parent Study and the Screening visit for this study will be solicited and recorded in the EDC to ensure continuity of safety follow-up from the Parent Study to this study. Events that occurred prior to dosing in this study will be recorded as medical history.

For subjects who received ARCT-021 in either the Parent Study or this study:

SAEs, NOCDs, CESIs, and MAAEs will be collected for all enrolled subjects for the duration of the study until the Final Visit (Day 365 or Day 281 if vaccinated or not vaccinated with ARCT-021 in this study) or Early Termination visit (if applicable).

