4.1 Changes to Cohort Nomenclature

The sub-cohort nomenclature will be modified for Cohort 1b and Cohort 2 in this SAP as shown in Section 5.2 to allow ease of interpretation of data.

4.2 Changes to Calculation of Day Since Study Day 1

Table 5 (which describes ‘Grouping of Cohorts and Timepoints Across Studies ARCT-021-01 and ARCT-021-02 for Analysis’) in Protocol Version 2.0 is modified to reflect the revised Cohort naming convention described above. The revised table is shown in Table 1:

Table 1: Grouping of Cohorts and Timepoints Across Studies ARCT-021-01 and ARCT-021-02 for Interim Analysis #1

Approximate timing:	Duration of Follow-up After Last Vaccination				
	15 days	1 month	2 months	6 months	12 months
Cohorts 1a and 1b	Day 15 in ARCT-021-02	Day 29 in ARCT-021-02	Day 57 in ARCT-021-02	Day 169 in ARCT-021-02	Day 365 in ARCT-021-02
Cohorts 2(A) to 2(D2)	Day 15 in ARCT-021-01	Day 29 in ARCT-021-01	Day 57 in ARCT-021-01	Day 29 in ARCT-021-02*	Day 197 in ARCT-021-02*
Cohorts 2(E) to 2(H)	Day 15 in ARCT-021-01	Day 29 in ARCT-021-01	Day 57 in ARCT-021-01	Day 29 in ARCT-021-01*	Day 197 in ARCT-021-02*

1 Month = 28 Days

*Follow-up Day in Study ARCT-021-02 is based on nominal day since Day 1 in Study ARCT-021-01. For Cohorts 2 (A to D2) the time enrolled in the Parent Study is 57 days and the time between Parent Study and Day 1 in Study ARCT-021-02 is nominally 90 Days. Therefore, Day 1 in Study ARCT-021-02 is $57 + 90 = 147$ days after Day 1 in the Parent Study. For Cohorts 2 (E to H), the time enrolled in the Parent Study is 85 days and the time between Parent Study and Day 1 in Study ARCT-021-02 is nominally 90 Days. Therefore, Day 1 in Study ARCT-021-02 is $85 + 90 = 175$ days after Day 1 in the Parent Study

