5.3.2 Study Day in Study ARCT-021-02

For Adverse events, Study day will be determined based on actual number of days since study Day 1. Study Day 1 will be identified from the CRF. For Cohort 1, it will be the day of vaccination. Study day for any given date will be:

- Given Date – Study Day 1 + 1 for dates on or after date of Study Day 1.
- Given Date – Study Day 1 for dates before date of Study Day 1.

For all immunogenicity data, the Study Day will be based on the nominal study day as captured in the CRF. For participants that received their first dose of ARCT-021 in the Parent study, nominal day since Day 1 in the Parent Study will also be displayed, as follows:

- For cohorts 1b (A to D2) and 2 (A to D2) Day 1 in Study ARCT-021-02 = Day 147 after Day 1 in the Parent Study, calculated as follows:
 - The time enrolled in the Parent Study is 57 days and the time between Parent Study and Day 1 in Study ARCT-021-02 is nominally 90 Days. Therefore, Day 1 in Study ARCT-021-02 is $57 + 90 = 147$ days after Day 1 in the Parent Study
- For cohorts 2 (E to H) Day 1 in Study ARCT-021-02 = Day 175 after Day 1 in the Parent Study, calculated as follows:
 - The time enrolled in the Parent Study is 85 days and the time between Parent Study and Day 1 in Study ARCT-021-02 is nominally 90 Days. Therefore, Day 1 in Study ARCT-021-02 is $85 + 90 = 175$ days after Day 1 in the Parent Study

Based on the above, in the Immunogenicity tables the visit name (when they are shown) will be displayed showing the nominal day from parent study within parenthesis. The nominal days will depend on the cohort and they will be as follows:

Table 3: Label for reporting Visit Days in safety and immunogenicity when needed.

Visit name in Protocol	Cohort			
	1a	1b	2 (A-D2)	2(E-H)
Day 1	Day 1	Day 1 (147)	Day 1 (147)	Day 1 (175)
Day 29	Day 29	Day 29 (175)	Day 29 (175)	Day 29 (203)
Day 43	Day 43	Day 43 (189)	Day 43 (189)	Day 43 (217)
Day 57	Day 57	Day 57 (203)	Day 57 (203)	Day 57 (231)
Day 85	Day 85	Day 85 (231)	Day 85 (231)	Day 85 (259)

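### Under one 12-month label, the SAE, MAAE and NOCD primary endpoints cover nominally 342 days after the last dose in Cohort 2 but 364 days in Cohort 1

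*Protocol*

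**What the plan says.** Protocol Section 10.5.3 lists the primary safety endpoints by cohort. For Cohort 2 (vaccinated in the parent study only) they are:

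- "SAEs through Day 197 (Cohort 2; 12 months after ARCT-021 vaccination in ARCT-021-01 study"
- "MAAEs through Day 197 (Cohort 2; 12 months after ARCT-021 vaccination in ARCT-021-01 study"
- "NOCDs through Day 197 (Cohort 2; 12 months after ARCT-021 vaccination in ARCT-021-01 study"

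For Cohort 1 (vaccinated in this study) the matching entry for serious events reads "SAEs through Day 365 (Cohort 1; 12 months after ARCT-021 vaccination in ARCT-021-02 study", and the MAAE and NOCD entries follow the same pattern. Protocol Table 5 and Section 10.5.4 also place Day 197 at 12 months for Cohort 2.

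The link between the two calendars is in the SAP. The footnote to SAP Table 1 says that "the time between Parent Study and Day 1 in Study ARCT-021-02 is nominally 90 Days". SAP Section 5.3.2 then sets "Day 1 in Study ARCT-021-02 = Day 147 after Day 1 in the Parent Study" for the single-dose cohorts A to D2 and "Day 1 in Study ARCT-021-02 = Day 175 after Day 1 in the Parent Study" for the two-dose cohorts E to H.

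Collection does not stop at Day 197. Under Protocol Section 6.2.1 these event types are recorded "until the Final Visit (Day 365 or Day 281 if vaccinated or not vaccinated with ARCT-021 in this study", so for Cohort 2 they run to Day 281.

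**The concern.** The protocol puts both cohorts' safety results under one label in one list. A reader will take the 12-month incidences of SAEs, MAAEs and NOCDs as covering equal time after vaccination, and as meeting the one-year observation rationale in Protocol Section 2.4. If Day 197 comes well before a year from the last dose, the Cohort 2 figure covers a shorter period than the Cohort 1 figure beside it. Safety is the primary objective, so the label on these endpoints should be exact. The events needed to complete the year are already being collected.

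**Working it through.** **Inputs**

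- Cut days: Day 197 for Cohort 2 and Day 365 for Cohort 1 (Protocol 10.5.3).
- Position of extension Day 1: parent Day 57 + 90 = 147 for A to D2, and parent Day 85 + 90 = 175 for E to H (SAP 5.3.2).
- Last dose, single-dose cohorts: parent Day 1.
- Last dose, two-dose cohorts: parent Day 29. This is inferred. Protocol Table 5 places parent Days 43, 57 and 85 at 15 days, 1 month and 2 months after the last dose, which matches Days 15, 29 and 57 in the single-dose cohorts, shifted by 28 days.

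**Formula**

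Parent day = (parent day of extension Day 1) + (extension day − 1). Days since last dose = parent day − parent day of last dose.

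**Day 197 in Cohort 2**

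- A to D2: 147 + 196 = parent Day 343; 343 − 1 = 342 days.
- E to H: 175 + 196 = parent Day 371; 371 − 29 = 342 days.
- SAP Section 7.2 numbers extension Day 29 as parent Day 176 or 204, one day later than SAP Table 3 (175 or 203). On that count both results are 343.

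**Day 365 in Cohort 1**

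- 365 − 1 = 364 days.

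**Difference**

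- Against Cohort 1: 364 − 342 = 22 days; 22/364 = 6.0%.
- Against 365 days: 365 − 342 = 23 days.

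**Can the 12-month label be reproduced?**

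| Month length | Cohort 2, Day 197 | Cohort 1, Day 365 |
|---|---|---|
| 28 days (footnote to SAP Table 1) | 342/28 = 12.2 | 364/28 = 13.0 |
| Calendar, 30.44 days | 342/30.44 = 11.2 | 364/30.44 = 12.0 |

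Each convention fits one cohort and misses the other. No single month length can make both windows exactly 12 months, because they would need months of 342/12 = 28.5 and 364/12 = 30.3 days.

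**Sensitivity to the gap between studies**

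With a gap of g days, Day 197 is 56 + g + 196 = 252 + g days after the last dose, in both single-dose and two-dose subjects. Reaching 364 or 365 days needs g = 112 or 113, rather than 90.

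**Where one year falls, and whether it is observed**

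- Nominally, 364 days is Day 197 + 22 = Day 219, and 365 days is Day 220.
- Day 281 is 342 + 84 = 426 days after the last dose.
- In general Day 281 is 56 + g + 280 = 336 + g days after the last dose, so a subject followed to Day 281 passes 364 days for any gap of 28 days or more.

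**The case against.** Several points on the other side have force.

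- **The gap is nominal.** Protocol Section 3.2 says only that subjects enter about three months after the last parent visit, and screening may take up to 28 days. If entry means consent at 90 days, Day 1 falls 90 to 118 days after the parent study, and Day 197 falls 342 to 370 days after the last dose. This stands as a limit on the figure for any one subject. It does not restore the label, because the SAP's own calendar puts Day 1 at 90 days and the protocol sets no gap that would equalise the windows.
- **The SAP defines a month as 28 days.** That brings Cohort 2 to 12.2 months but takes Cohort 1 to 13.0, so it does not reconcile the list in Section 10.5.3.
- **The endpoint says vaccination, not last dose.** Counted from the first dose, two-dose subjects reach 371 − 1 = 370 days at Day 197. However, Protocol Sections 3.7, 10.2 and 10.5.4 count from the last injection or dose, and single-dose Cohort 2 subjects fall short either way.
- **The analysis is descriptive.** No error rate or sample size is affected, and follow-up to Day 281 meets the commitment to at least 12 months on the nominal calendar.

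A reader might infer two stronger things that the documents do not support.

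- One is that Cohort 2 events after Day 197 are lost. The formal primary endpoint in Protocol Section 1.2.1 has no Day 197 limit, and the synopsis tabulates all TEAEs. SAP Section 8 runs these events to the off-study vaccine or the interim data cut. SAP Section 8.1.9.1 covers unsolicited events up to end of study or off-study vaccination. SAP Sections 8.1.4 to 8.1.6 provide listings and narratives.
- The other is that the ±14-day window on the Day 197 visit lets the cut slide earlier. SAP Section 5.3.2 counts adverse-event study day from actual dates, so the attendance date does not move a cut on onset day.

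**Conclusion.** The point holds as a mismatch of windows under one label. In Protocol Section 10.5.3 the Cohort 2 SAE, MAAE and NOCD endpoints nominally end 342 days after the last dose (343 on the SAP's alternative count), while the Cohort 1 endpoints end at 364. The shortfall is about 22 days, or 6%, against Cohort 1, and 23 days against 365.

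This rests on the SAP's nominal 90-day gap and, for cohorts E to H, on a second dose at parent Day 29 inferred from Protocol Table 5. Actual values will differ between subjects.

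Cohort 2 events from Day 198 to Day 281 lie outside the named endpoints in Section 10.5.3, but remain available to the general TEAE tables, listings and narratives. The effect is on the meaning and comparability of a descriptive incidence. It is still worth correcting, because the endpoint is primary and the data to deliver it are already being collected.

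**What to change.** In Protocol Section 10.5.3, define the 12-month SAE, MAAE and NOCD endpoints for both cohorts as events with onset within the same number of days of the subject's actual last ARCT-021 dose date. Either 364 or 365 would do; 364 leaves the Cohort 1 cut where it is. State in the same section that Cohort 2 events through Day 281 are also summarised. Use the same definition for the supporting summary in Section 10.5.3 that runs to 12 months without giving days, and carry it into the SAP for the final analysis. The SAP's censoring at off-study vaccination can stay as written.

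The cost is a change of wording and one derived date per subject. No visits or new data are required.

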1.2 Study Endpoints

1.2.1 Primary Endpoint(s)

The safety and reactogenicity of ARCT-021 will be assessed by determining the incidence, severity, and dose-relationship of solicited local and systemic adverse events, unsolicited adverse events (including serious adverse events (SAEs), new onset of chronic disease (NOCDs), medically attended adverse events (MAAEs), changes in vital signs and changes in the laboratory parameters by dose.

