3.8.2 Study Drug Administration

Subjects receiving a single injection of ARCT-021

ARCT-021 will be administered on Day 1 following Baseline evaluations. Subjects will be observed for at least 30 minutes after dosing. After this, subjects may remain at the study center or be discharged.

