9. Has any blood dyscrasias or significant disorder of coagulation.
10. Uncontrolled hypertension (BP > 160/100 mm Hg)
11. Treatment with another investigational drug, biological agent, or device since completion of the Parent Study
12. Received or plans to receive:
 - A licensed, live vaccine within 4 weeks before or after study vaccination, or

- A licensed, inactivated vaccine within 2 weeks before or after study vaccination.

13. Has traveled outside of Singapore within 30 days before the vaccination or planned travel outside of Singapore within 60 days after vaccination.

14. Have any other conditions, which, in the opinion of the Investigator or Sponsor would make the subject unsuitable for inclusion, or could interfere with the subject participating in or completing the Study

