2.2 Endpoints

2.2.1 Primary Endpoint

The safety and reactogenicity of ARCT-021 will be assessed by determining the incidence, severity, and dose-relationship of solicited local and systemic adverse events, unsolicited adverse events (including serious adverse events (SAEs)), and changes in Laboratory Toxicity Results.

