8. SAFETY ANALYSIS

The primary objective of the study is the evaluation of the safety of ARCT-021. The primary endpoints that align with this objective are:

- Solicited AEs for 7 days after vaccination with ARCT-021 (Cohort 1 only).
- Unsolicited AEs within 28 days after vaccination with ARCT-021 (Cohort 1 only), summarized by mild/moderate/severe and relationship to ARCT-021.
- SAEs, MAAEs, NOCD and AE leading to discontinuation/withdrawal according to the following windows
 - Pre-Study for cohort 1b
 - Within 28 days after vaccination with ARCT-021 (Cohort 1 only)
 - from 28 days after vaccination to the last observation prior to receipt of off study vaccine or prior the data cut point for this interim, whichever is first (all cohorts/sub-cohorts).
- Safety laboratory assessments through 28 days after vaccination with ARCT-021 (Cohort 1 only), summarized by toxicity grade (where relevant).
- Vital signs assessments through the last observation prior to receipt of off study vaccine or prior to the data cut point for this interim, whichever is first, summarized by toxicity grade.
- Unsolicited AEs, MAAEs, SAEs and vital signs assessments from after receipt of off-study vaccine up to the observation prior to the data cut point for this interim.

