Assessment after Screening Period

Participants Not receiving ARCT-021 in This Study.

Study Week/Day	Observation Period (40 Weeks)				
	W1 D1	W5 D29	W13 D85	W29 D197	W41 D281/or Early Term*
Visit Window (Days)	0	± 7	± 7	± 14	± 14
Physical Exam ¹	X		X	X	X
Vital Sign ²	X		X	X	X
Archived plasma sample ³	X	X	X	X	X
Archived serum sample ³	X	X	X	X	X
Archived PBMC sample ³	X	X	X	X	X
Immunogenicity		X		X	X
T-cell response		X		X	X
SAE, CESI, NOCD and MAAE ⁴	X	X	X	X	X
SARS-CoV-2 questioning ⁵	X	X	X	X	X
Counselling about long term follow-up for SARS-CoV-2 infection ⁶					X

* Participants that terminate early should complete all procedures for Study Day 281

1 Abbreviated physical exam (assessment of vitals, heart, lungs, lymphatic, abdomen and symptoms directed examination, if any symptom) to be given during observation period to assess changes from screening.

2 BP, HR RR, temp.

3 Stored at -70°C for follow up immunological assessment or exploration of laboratory findings and/or adverse events.

4 SAE, CESI, NOCD and MAAE will be recorded.

5 At each visit participants will be questioned about symptoms of COVID-19 and exposure to confirmed COVID-19 or confirmed SARS-COV-2 infection cases amongst household contacts, friends, work contacts and other contacts.

6 Participants that terminate from the study before completion will be told to inform the study site staff if they develop symptoms compatible with COVID-19 (Section 6.2.4), or a diagnosis of SARS-CoV-2 infection or COVID-19 for one year after vaccination so that they can be adequately followed up.

Participants Receiving a Single Injection of ARCT-021 in This Study.

Study Week/Day	Study vaccine Administration	Post-Treatment Period (52 Weeks)						
		W2 D8	W3 D15	W5 D29	W9 D57	W25 D169	W37 D253	W53 D365/ Early Term*
Visit Window (Days)	0	±1	±1	0	±7	±14	±14	±14
Physical Exam ¹	X ^a	X	X	X	X	X	X	X
Vital Sign ²	X ^a	X	X	X	X	X	X	X
Pregnancy Test ³	X ^a							
Chemistry Panel	X ^a	X	X	X				
Hematology	X ^a	X	X	X				
Coagulation	X ^a							
HbA1c	X ^a							
Urinalysis ⁴	X ^a	X		X				
Archived plasma sample ⁵	X ^a			X	X	X	X	X
Archived serum sample ⁵	X ^a			X	X	X	X	X
Archived PBMC sample ⁵	X ^a		X	X	X	X	X	X
Immunogenicity	X ^a			X	X	X		X
T-cell responses	X ^a		X	X		X		X
Drug/Alcohol Screen ⁶	X ^a							
Study vaccine Administration	X							
Review of symptom Diary ⁷		X	X					
Unsolicited AE	X	X	X	X				
SAE, CESI, NOCD and MAAE ⁸	X	X	X	X	X	X	X	X
Concomitant Medications and Procedures	X	X	X	X				

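### Vital signs are a primary safety endpoint worded as change, but are summarised only by toxicity grade, without the baseline-to-maximum grade shift that the SAP gives laboratory data

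*Protocol*

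**What the plan says.** Protocol 1.2.1 ends its list of primary safety measures with "changes in vital signs and changes in the laboratory parameters by dose". Protocol 10.5.3 lists vital signs among the primary endpoints, to be presented as "Vital signs assessments through day 365 (Cohort 1; 12 months after ARCT-021 vaccination in ARCT-021-02 study) summarized by toxicity grade".

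SAP 8 keeps them in its own list of primary endpoints, as "Vital signs assessments through the last observation prior to receipt of off study vaccine or prior to the data cut point for this interim", again by toxicity grade. SAP 2.2.1, however, states the primary endpoint without vital signs: it ends with "unsolicited adverse events (including serious adverse events (SAEs)), and changes in Laboratory Toxicity Results".

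SAP 8.2 specifies shift tables, grade at baseline against maximum grade after vaccination, for laboratory parameters on the toxicity scale. No SAP subsection does the same for vital signs.

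The schedule for dosed subjects (SAP Appendix A, "Participants Receiving a Single Injection of ARCT-021 in This Study") marks vital signs pre-dose on Day 1 and then at each visit from Day 8. The set is blood pressure (BP), heart rate (HR), respiratory rate (RR) and temperature.

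**The concern.** A table of grades after vaccination shows how many subjects had an abnormal value. It does not show how many had a change, and the endpoint is worded as change. A subject with raised blood pressure before the injection and the same pressure afterwards counts in such a table exactly as a subject whose pressure rose. Entry allows for this: subjects to be dosed are excluded for "Uncontrolled hypertension (BP > 160/100 mm Hg"), so readings up to that limit can be present at baseline.

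There is no concurrent control group to show the background rate, so each subject's own pre-dose value is the only reference available. SAP 4 says that the interim analysis supports a regulatory filing. A grade table without the baseline grade could mislead there in either direction: stable abnormalities could look like vaccine effects, or real worsening could be set aside as probably pre-existing.

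**Working it through.** The documents give no figure to reproduce on this point. The check sets the provisions side by side, counts the visits and illustrates the size under stated assumptions.

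**1. Laboratory data against vital signs**

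| | Laboratory | Vital signs |
|---|---|---|
| Primary endpoint as change, Protocol 1.2.1 | Yes | Yes |
| Named in SAP 2.2.1 | Yes | No |
| Listed by toxicity grade in SAP 8 | Yes | Yes |
| Own analysis subsection | SAP 8.2 | None |
| Baseline-to-maximum grade shift | Yes, for parameters worsening within 7 days | None specified |

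**2. What the general rules add**

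- SAP 5.3.1 defines the Safety Population baseline as the last value before ARCT-021 in this study, so the reference exists.
- SAP 6.2 lists and summarises baseline vital signs, but as a baseline characteristic.
- SAP 5 promises change-from-baseline statistics in general, without naming the variables. Even if applied to vital signs, these are means, medians and ranges. They do not show which grades are new, worsened or persisting.

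**3. Timing of readings in dosed subjects**

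- Visits with vital signs: Day 1 (pre-dose), 8, 15, 29, 57, 169, 253 and 365. That is 8 − 1 = 7 post-dose sets.
- First post-dose set: Day 8 − Day 1 = 7 days after injection; with the ±1 day window, 6 to 8 days.
- BP, HR or RR sets scheduled between the pre-dose reading and that visit: 0. Protocol 3.8.2 says "Subjects will be observed for at least 30 minutes after dosing", but names no reading in that time.
- Temperature differs. Protocol 6.2.1 has it recorded daily in the diary for 7 days and graded from 38 °C, and SAP 8.1.9.2 tabulates solicited fever by day from Day 1 to Day 7.

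The vital-sign row in the protocol's schedule, as extracted, shows one mark more than there are visits. The SAP copy has eight marks for eight visits and agrees with the visit list in Protocol 3.8.3, so I used that.

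**4. Illustration of size**

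The documents give neither the prevalence of a graded value at baseline (p) nor the size of Cohort 1 (n). Both are assumed; 99 is the approximate total enrolment in Protocol 3.6, so it is high for a subset. With no vaccine effect and baseline grades that persist, the expected number of subjects shown as graded is n × p:

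| n | p = 5% | p = 10% | p = 20% |
|---|---|---|---|
| 20 | 1.0 | 2.0 | 4.0 |
| 50 | 2.5 | 5.0 | 10.0 |
| 99 | 5.0 | 9.9 | 19.8 |

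The chance of at least one such subject is 1 − (1 − p)^n. For n = 20 that is 64% at p = 5% and 88% at p = 10%; for n = 50 it is 92% and over 99%. In a shift table all of these subjects would fall in the unchanged cells.

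A second source of grades is chance. If a normal subject exceeds a cut-off at any one visit with probability q, independently across visits, the chance of at least one grade over 7 visits is 1 − (1 − q)^7: 7%, 19% or 30% for q = 1%, 3% or 5%. A shift to the maximum grade does not remove this, which is why change by visit should stand beside it.

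**The case against.** The strongest reply is that the baseline comparison is mostly in the plan already: a safety baseline is defined, baseline vital signs are summarised, and SAP 5 has a general change-from-baseline rule. The output shells are not in the documents and might contain a shift table. Protocol 9.4 treats pre-existing conditions as medical history unless they worsen, so adverse event counts are protected. The toxicity scale's cut-offs are not in the documents either, so it cannot be shown which blood pressures admitted at entry would be graded. Finally, this SAP covers one interim analysis.

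Most of this stands, and it limits the point. It leaves one gap: the only presentation specified for this endpoint is a grade tabulation, and nothing in the text separates new or worsened grades from persisting ones, although the SAP does so for laboratory grades.

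A reader might also infer from the schedule that an acute vaccine effect could not be seen at all. The documents do not support that. Temperature is covered daily, unsolicited events are collected from the injection onward, and Protocol 8.3 has further assessments discussed with the medical monitor after a severe reaction. The unassessed part is asymptomatic change in BP, HR and RR before Day 8.

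Nor do the documents support adding a reading at the end of the 30-minute observation. In the rabbit data of Protocol 2.5.3, cytokines were raised at 6 hours and CRP peaked at 48 hours, both later than such a reading. Dosing also appears complete: SAP 4.4 has Day 57 immunogenicity data for Cohort 1, and SAP 8.1.9.3 speaks of the 28-day collection period as past.

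**Conclusion.** The point holds as a gap in the specified analysis. One primary safety endpoint, worded as change, is to be shown by grade only, so pre-existing grades can appear as new ones in that table. The adverse event and fever tables are not affected.

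The size cannot be fixed from the documents. Under the assumed prevalences of 5% to 20% it is 1 to 4 subjects per 20 dosed, which could dominate a small table. The conclusion assumes that some dosed subjects have a graded value at baseline and that the unseen output shells contain no shift table for vital signs.

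It does not follow that the study cannot describe changes in vital signs. The pre-dose and post-dose readings are collected, and only the presentation is missing. A clean table would, however, say nothing about BP, HR and RR in the first 6 to 8 days after injection.

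**What to change.** 1. In SAP 8, and in the final SAP, add a vital-sign table for Cohort 1: grade at baseline (last pre-dose value) against maximum post-dose grade, with new or worsened grades counted. Use observations before any off-study vaccine, in line with SAP 5.3.3.
2. State that the change-from-baseline summaries in SAP 5 apply to BP, HR, RR and temperature, by visit.
3. Add a note to the table: no BP, HR or RR was scheduled between dosing and Day 8 (6 to 8 days after injection), so acute asymptomatic changes in these were not assessed. Temperature in that period is covered by the daily diary and the solicited fever tables.
4. Reconcile SAP 2.2.1 with SAP 8 and Protocol 1.2.1 on whether vital signs are a primary endpoint.

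SAP 5.1 allows no change to the interim plan once the data are pulled. If that has happened, put the table in the final SAP and label any interim version as added afterwards. The cost is one extra table and its programming, from data already collected, with no new procedure or visit.
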